**SET B :**

**You are stuck behind a slow driver on an otherwise open road.**

- |  | Very Unlikely | Unlikely | Somewhat Likely | Likely | Very Likely |
|--|---------------|----------|-----------------|--------|-------------|
|--|---------------|----------|-----------------|--------|-------------|

- |   |                       |                       |                       |                       |                       |
|---|-----------------------|-----------------------|-----------------------|-----------------------|-----------------------|
| 25. Now I'll never get where I'm going!                   |  |  |  |  |  |
| 26. People need to learn to drive!                        |  |  |  |  |  |
| 27. People are always slowing me down/getting in my way.  |  |  |  |  |  |
| 28. He/she's doing this just to make me mad.              |  |  |  |  |  |
| 29. What a dumb-ass/lowlife/idiot!                        |  |  |  |  |  |
| 30. Getting angry isn't going to get me there any sooner. |  |  |  |  |  |

**You are at a store waiting to be helped, but the clerks are talking to each other and ignoring you.**

- |  | Very
Unlikely      | Unlikely              | Somewhat
Likely    | Likely                | Very
Likely        |
|--|-----------------------|-----------------------|-----------------------|-----------------------|-----------------------|
| 31. These lazy jerks/bitches/idiot!  |  |  |  |  |  |
| 32. Getting angry isn't going to get me out of here any sooner.  |  |  |  |  |  |
| 33. They're probably ignoring me on purpose just so they don't have to do their job.                       |  |  |  |  |  |
| 34. This is terrible. I'm never going to get out of here.  |  |  |  |  |  |
| 35. People are so rude. / People like this always slow me down. / Nobody cares about the customer anymore. |  |  |  |  |  |
| 36. I don't care what they are talking about. They need to get over here and help me now.                  |  |  |  |  |  |

**Your spouse/significant other doesn't do something he/she promised he/she would take care of.**

- |   | Very
Unlikely      | Unlikely              | Somewhat
Likely    | Likely                | Very
Likely        |
|---|-----------------------|-----------------------|-----------------------|-----------------------|-----------------------|
| 37. He/she can be so stupid/worthless/irresponsible sometimes.                                  |  |  |  |  |  |
| 38. I can never count on him/her. / He/she always forgets to do things.                         |  |  |  |  |  |
| 39. He/she should know better than this.  |  |  |  |  |  |
| 40. This is a catastrophe! / I can't believe this is happening. / I can't trust him/her at all. |  |  |  |  |  |
| 41. He/she knew this was important to me and didn't do it anyway. /                             |  |  |  |  |  |

He/she isn't taking me seriously. /  
He/she is trying to get back at me  
for something.

- |  |                       |                       |                       |                       |                       |
|--|-----------------------|-----------------------|-----------------------|-----------------------|-----------------------|
| 42. I'm sure there must have been a good reason why he/she didn't get this done. |  |  |  |  |  |
|--|-----------------------|-----------------------|-----------------------|-----------------------|-----------------------|

**Someone talks down/is condescending to you.**

- |  | Very
Unlikely      | Unlikely              | Somewhat
Likely    | Likely                | Very
Likely        |
|--|-----------------------|-----------------------|-----------------------|-----------------------|-----------------------|
| 43. I can't stand having to hear this.   |  |  |  |  |  |
| 44. People are so rude. / He/she always acts this way.   |  |  |  |  |  |
| 45. He/she just thinks he/she's better than me. / I know he/she is just trying to make me upset. |  |  |  |  |  |
| 46. I hate this arrogant/conceited/stuck-up loser!   |  |  |  |  |  |
| 47. I shouldn't have to listen to this. / People can't talk to me this way.                      |  |  |  |  |  |
| 48. Even though I don't like hearing this, I can't control what others say to me.                |  |  |  |  |  |

**Your family doesn't take your education/career seriously.**

- |  | Very
Unlikely      | Unlikely              | Somewhat
Likely    | Likely                | Very
Likely        |
|--|-----------------------|-----------------------|-----------------------|-----------------------|-----------------------|
| 49. They just don't care about what's important to me.                                       |  |  |  |  |  |
| 50. I can't deal with it when they act this way.   |  |  |  |  |  |
| 51. I don't deserve to be treated this way. / They should just be quiet and leave me alone.  |  |  |  |  |  |
| 52. They can be so cruel/nasty/selfish sometimes.  |  |  |  |  |  |
| 53. People never understand me. / I always have to put up with things like this from people. |  |  |  |  |  |
| 54. I can't expect them to agree with everything I do or say.                                |  |  |  |  |  |

Scoring: Missattributin g Causation	Catastroph i Evaluating	Overgeneralizing	Demandingne ss	Inflammator y Labeling	Adaptiv e
1	2	3	5	6	4
7	8	12	9	11	10
16	14	13	18	17	15
21	22	23	20	19	24
28	25	27	26	29	30
33	34	35	36	31	32
41	40	38	39	37	42
45	43	44	47	46	48
49	50	53	51	52	54

Scoring instructions: Convert scaled responses to numbers as follows:

Very unlikely: 1

Unlikely: 2

Somewhat likely: 3

Likely: 4

Very likely: 5

Sum responses for each of the six subscales for overall score on each subscale. Item number legend for subscales provided in the table above.

## Appendix D

### Demographics Questions

**Instructions:** Please respond to each of the following questions.

1. What is your age: \_\_\_\_\_
2. What is your gender:
  - a. Male
  - b. Female
  - c. Prefer not to say
3. Please select your highest level of education:
  - a. None
  - b. Less than High School
  - c. High School Graduate, diploma or equivalent
  - d. Some college credit, no degree
  - e. Trade/technical/vocational training
  - f. Associates Degree
  - g. Master's Degree
  - h. Professional Degree
  - i. Doctorate Degree
  - j. Other

## Appendix E

### HBMT Stimuli and Instructions

#### Real Training:

You will be presented with words with some letters missing (e.g., AP\_LE). These can be completed to form either negative, or non-negative (i.e. positive or neutral) themed words. Some fragments could be completed to form more than one type of word.

Your job is to complete the word fragments to make positive and/or neutral themed words. When a word fragment appears on your screen (e.g., KI\_\_), try to think of either a positive (e.g., KISS) or neutral (e.g., KITE) word that can be made by completing the fragment. As soon as you think of one, type the complete word into the text box and press enter. If the fragment can ONLY be completed to form a negative word (e.g., "KI\_L" can only form "KILL"), then do not press anything and let the clock expire. You will have 12 seconds to respond. Please try to respond as quickly and as accurately as possible. The first five trials are for practice only and will not be recorded for data.

#### Fake-Training

You will be presented with words with some letters missing (e.g., AP\_LE). Your job is to complete the fragment to form a complete word. When a word fragment appears on your screen (e.g., KI\_\_), try to think of a word that completes the fragment (e.g., KILT). As soon as you think of one, please type the complete word into the text box and press enter. You will have 12 seconds to respond. Please try to respond as quickly and as accurately as possible. The first five trials are for practice only and will not be recorded for data.

#### Stimuli:

Stem Type	Stem	(Possible) Solutions
1. (P) Positive/Neutral	SYM__HY	SYMPATHY
2. Positive/Neutral	COM__SS_ON	COMPASSION/COMMISSION
3. (P) Positive/Neutral	WI__POWE_	WILLPOWER
4. Positive/Neutral	ME_CY	MERCY
5. Positive/Neutral	DISCI_LINE_	DISCIPLINED
6. Positive/Neutral	MORA_	MORAL/MORAY/MORAS
7. Positive/Neutral	FR__ND	FRIEND
8. Positive/Neutral	PEA__UL	PEACEFUL
9. Positive/Neutral	PR_D_NT	PRUDENT
10. Positive/Neutral	NIC_	NICE
11. Positive/Neutral	P_SI_IVE	POSITIVE

12. Positive/Neutral	T_L_RATE	TOLERATE
13. Positive/Neutral	C_NSID__ATE	CONSIDERATE
14. Positive/Neutral	G_N_LE	GENTLE
15. Positive/Neutral	CA_M	CALM
16. Positive/Neutral	FA_R	FAIR
17. Positive/Neutral	G__D	GOOD/GLAD/GRAD/GRID/GILD/GOLD
18. Positive/Neutral	_ENEROU_	GENEROUS
19. Positive/Neutral	__LAX_D	RELAXED
20. Positive/Neutral	AC_EPT__G	ACCEPTING
21. (P) Negative	E_IL	EVIL
22. (P) Negative	TOR_U_E	TORTURE
23. Negative	REV_N_E	REVENGE
24. Negative	AN_OY	ANNOY
25. Negative	VIC_O_S	VICIOUS
26. Negative	E_EM_	ENEMY
27. Negative	VILL____	VILLAIN
28. Negative	B__TAL	BRUTAL
29. Negative	HE__ISH	HELLISH
30. Negative	DESTRC__IVE	DESTRCUTIVE
31. Negative	AB__DON	ABANDON
32. Negative	RID__ULE	RIDICULE
33. Negative	EX__UTE	EXECUTE
34. Negative	C__RCE	COERCE
35. Negative	W__PON	WEAPON
36. Negative	__OOT	SHOOT
37. Negative	B__RAY	BETRAY
38. Negative	CA__OUS	CALLOUS
39. Negative	INH__ANE	INHUMANE
40. Negative	LIA_	LIAR
41. (P) Ambiguous	_UNCH	PUNCH/LUNCH/MUNCH/BUNCH
42. (P) Ambiguous	__ __ENSIVE	OFFENSIVE/EXTENSIVE/ EXPENSIVE/DEFENSIVE
43. (P) Ambiguous	PERSE__ _E	PERSECUTE/PERSEVERE
44. Ambiguous	R__ _LESS	RESTLESS/RUTHLESS
45. Ambiguous	REJ__ __	REJOIN/REJECT
46. Ambiguous	SM__ __	SMILE/SMACK/SMART/ SMOKE/SMITH/SMOTE/SMITE

47. Ambiguous	__ SULT	INSULT/RESULT
48. Ambiguous	HEART_____	HEARTLESS/HEARTFULL
49. Ambiguous	__ CLUDED	EXCLUDED/INCLUDED
50. Ambiguous	HEL_	HELL/HELP/HELD/HELM
51. Ambiguous	_ ATE	HATE/MATE/RATE/FATE/TATE/BATE
52. Ambiguous	HU__	HURT/HUGS/HUNG/HULE/HUED/ HUNK/HUNT/HUMP/HUGE/HURL
53. Ambiguous	ME__	MEAN/MEAL/MEAT/MEME/MEAD/ MELT/MENT/MEOW/MEND
54. Ambiguous	CR__L	CRUEL/CRAWL
55. Ambiguous	PROV__E	PROVOKE/PROVIDE
56. Ambiguous	A_USE	ABUSE/AMUSE/ACUSE
57. Ambiguous	KI__	KISS/KILL/KICK/KILT
58. Ambiguous	B__ TER	BITTER/BETTER/BUTTER
59. Ambiguous	H___FUL	HURTFUL/HELPFUL/HOPEFUL/ HANDFUL/HARMFUL/HATEFUL
60. Ambiguous	___ MENT	TORMENT/AUGMENT/PAYMENT/ RAIMENT/SARMENT/SEGMENT/ ODDMENT/GARMENT/AUGMENT/ CLEMENT/FIGMENT/FERMENT/ ELEMENT/AILMENT
61. Ambiguous	___ EFUL	SPITEFUL/HOPEFUL/DOLEFUL/ FATEFUL/WAKEFUL/BANEFUL/ HATEFUL
62. Ambiguous	W__KED	WICKED/WALKED/WINKED/WORKED
63. Ambiguous	HOSTI__	HOSTILE/HOSTING
64. Ambiguous	___ GIVE	FORGIVE/MISGIVE
65. Ambiguous	STR__E	STRIVE/STRIKE/STRAFE/STRIFE/ STRIDE/STROBE/STROKE/STROVE/ STRIPE/STRIVE
66. Ambiguous	ATTA__	ATTACH/ATTACK
67. Ambiguous	EXPLO_E	EXPLODE/EXPLORE
68. Ambiguous	ANGE_	ANGER/ANGEL
69. Ambiguous	INS__T	INSULT/INSECT/INSERT
70. Ambiguous	SM_CK	SMACK/SMOCK
71. Ambiguous	R_DE	RUDE/RIDE
72. Ambiguous	_ IGH T	FIGHT/SIGHT/RIGHT/ BIGHT/EIGHT/TIGHT

73. Ambiguous	EN_AGE	ENRAGE/ENGAGE
74. Ambiguous	MU__ER	MURDER/MUTTER/MUSTER/MUCKER/ MUDDER/MUMMER/MUNTER
75. Ambiguous	OFF___	OFFEND/OFFICE/OFFERS/ OFFISH/OFFSET
76. Ambiguous	_OCK	MOCK/SOCK/COCK/DOCK/ JOCK/LOCK/NOCK
77. Ambiguous	P___FUL	PAINFUL/PLAYFUL/PITIFUL/ PALMFUL/PAILFUL
78. Ambiguous	BU__Y	BULLY/BUDDY
79. Ambiguous	MIS_EAD	MISLEAD/MISREAD
80. Ambiguous	FOR___E	FORGIVE/FORSAKE
81.		

Note: (P) indicates practice trial.

**Appendix F**

## State Aggression Questionnaire

Please indicate how often you have done each behavior during the past **24 hours**.

During the **PAST 24 HOURS**, how often have you:

Get angry with someone and yell or shout at them.

1 = Never      2 = One Time      3 = Two Times      4 = Three or Four Times      5 = Five or more times

Get angry with someone and kick or smash something, slam the door, punch the wall, etc.

1 = Never      2 = One Time      3 = Two Times      4 = Three or Four Times      5 = Five or more times

The following set of questions is asking about your **ONLINE BEHAVIOR OVER THE PAST 24 HOURS**.

I have removed or refused another person on a contact list for a chat, social network, or instant messaging program, without him/her doing anything and only for being who he/she was

1 = Never      2 = One Time      3 = Two Times      4 = Three or Four Times      5 = Five or more times

I have posted rude or unfriendly comments about someone on social networks.

1 = Never      2 = One Time      3 = Two Times      4 = Three or Four Times      5 = Five or more times

I have insulted someone using text messages or instant messaging programs (e.g., WhatsApp, SMS).

1 = Never      2 = One Time      3 = Two Times      4 = Three or Four Times      5 = Five or more times

I have made a false complaint about someone on a forum, social network, or online game.

1 = Never      2 = One Time      3 = Two Times      4 = Three or Four Times      5 = Five or more times

I have plotted with other people to ignore someone on social networks.

1 = Never      2 = One Time      3 = Two Times      4 = Three or Four Times      5 = Five or more times

I have posted or shared rumors or negative comments or negative news about someone on a social network

1 = Never      2 = One Time      3 = Two Times      4 = Three or Four Times      5 = Five or more times

\*I have “liked”, shared, or otherwise demonstrated support for negative content about another person online or on social media.

1 = Never      2 = One Time      3 = Two Times      4 = Three or Four Times      5 = Five or more times

The following questions are asking about your **DRIVING BEHAVIORS OVER THE PAST 24 HOURS**

Have you driven in the past 24 hours: Yes/No

I have called other drivers names aloud (e.g., “Jerk!”, “Idiot!”)

1 = Never      2 = One Time      3 = Two Times      4 = Three or Four Times      5 = Five or more times

I have made negative comments about other drivers

1 = Never      2 = One Time      3 = Two Times      4 = Three or Four Times      5 = Five or more times

I have yelled questions like “Where did you learn how to drive!?”

1 = Never      2 = One Time      3 = Two Times      4 = Three or Four Times      5 = Five or more times

I have glared at other drivers.

1 = Never      2 = One Time      3 = Two Times      4 = Three or Four Times      5 = Five or more times

I have called other drivers mean names under my breath.

1 = Never      2 = One Time      3 = Two Times      4 = Three or Four Times      5 = Five or more times

I have sworn at other drivers aloud.

1 = Never      2 = One Time      3 = Two Times      4 = Three or Four Times      5 = Five or more times

I have sworn at other drivers under my breath.

1 = Never      2 = One Time      3 = Two Times      4 = Three or Four Times      5 = Five or more times

I have shaken my head or made other negative gestures at other drivers.

1 = Never      2 = One Time      3 = Two Times      4 = Three or Four Times      5 = Five or more times

I have yelled at other drivers.

1 = Never      2 = One Time      3 = Two Times      4 = Three or Four Times      5 = Five or more times

I have made negative comments about other drivers under my breath.

1 = Never      2 = One Time      3 = Two Times      4 = Three or Four Times      5 = Five or more times

I have given other drivers a dirty look.

1 = Never      2 = One Time      3 = Two Times      4 = Three or Four Times      5 = Five or more times

I have thought negative things about other drivers like “Where did you get your license?”

1 = Never      2 = One Time      3 = Two Times      4 = Three or Four Times      5 = Five or more times

Items adapted from:

Álvarez-García, D., Barreiro-Collazo, A., Núñez, J. C., & Dobarro, A. (2016). Validity and Reliability of the Cyber-aggression Questionnaire for Adolescents (CYBA). *The European Journal of Psychology Applied to Legal Context*, 8(2), 69-77.

Deffenbacher, J. L., Lynch, R. S., Deffenbacher, D. M., & Oetting, E. R. (2001). Further evidence of reliability and validity for the Driving Anger Expression Inventory. *Psychological Reports*, 89, 535-540.

Deffenbacher, J. L., Lynch, R. S., Oetting, E. R., & Swaim, R. C. (2002). The Driving Anger Expression Inventory: A measure of how people express their anger on the road. *Behaviour Research and Therapy*, 40, 717-737.

\*Indicates an item created by the PI and added to the study.

**Appendix G**

Trait anger Questionnaire

**I am a hotheaded person.**

1 = Strongly Disagree	2	3	4	5 = Strongly Agree
--------------------------	---	---	---	-----------------------

**I have a fiery temper.**

1 = Strongly Disagree	2	3	4	5 = Strongly Agree
--------------------------	---	---	---	-----------------------

Citation: Wilk, J. E., Quartana, P. J., Clarke-Walper, K., Kok, B. C., & Riviere, L. A. (2015). Aggression in US soldiers post-deployment: Associations with combat exposure and PTSD and the moderating role of trait anger. *Aggressive behavior*, 41(6), 556-565.

**Appendix H**

## State Emotion Questionnaire

How well do the following statements describe how you have **FELT OVER THE PAST 24 HOURS?**

I have felt angry.

1 = Extremely uncharacteristic of me.	2	3	4	5 = Extremely characteristic of me.
---------------------------------------	---	---	---	-------------------------------------

I have felt joyful.

1 = Extremely uncharacteristic of me.	2	3	4	5 = Extremely characteristic of me.
---------------------------------------	---	---	---	-------------------------------------

I have felt stressed.

1 = Extremely uncharacteristic of me.	2	3	4	5 = Extremely characteristic of me.
---------------------------------------	---	---	---	-------------------------------------

I have been energetic.

1 = Extremely uncharacteristic of me.	2	3	4	5 = Extremely characteristic of me.
---------------------------------------	---	---	---	-------------------------------------

I have been relaxed.

1 = Extremely uncharacteristic of me.	2	3	4	5 = Extremely characteristic of me.
---------------------------------------	---	---	---	-------------------------------------

I have gotten frightened easily.

1 = Extremely uncharacteristic of me.	2	3	4	5 = Extremely characteristic of me.
---------------------------------------	---	---	---	-------------------------------------

I have gotten irritated easily.

1 = Extremely uncharacteristic of me.	2	3	4	5 = Extremely characteristic of me.
---------------------------------------	---	---	---	-------------------------------------

I have not been easily annoyed.

1 = Extremely  
uncharacteristic  
of me.

2

3

4

5 = Extremely  
characteristic of  
me.

Citation: Goldberg, L. R. (1999). A broad-bandwidth, public domain, personality inventory measuring the lower-level facets of several five-factor models. In I. Mervielde, I. Deary, F. De Fruyt, & F. Ostendorf (Eds.), *Personality Psychology in Europe*, Vol. 7 (pp. 7-28). Tilburg, The Netherlands: Tilburg University Press.

Goldberg, L. R., Johnson, J. A., Eber, H. W., Hogan, R., Ashton, M. C., Cloninger, C. R., & Gough, H. C. (2006). The International Personality Item Pool and the future of public-domain personality measures. *Journal of Research in Personality*, 40, 84-96.

Quartana, P. J., & Burns, J. W. (2007). Painful consequences of anger suppression. *Emotion*, 7(2), 400-414.

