#### 3.3 Study Design, Methodology, and Experimental Manipulations

The study consists of a two group design. Assignment to each of the two experimental conditions is determined randomly upon the volunteers’ arrival to the study webpage. However, the website will be programmed to achieve equal sample size across the two groups. The duration of participation for each volunteer is estimated to be about 60 minutes (total, including both time-points). Volunteers will complete the following as part of the study:

- a. HBMT: Volunteers will complete a computer-based hostile bias modification training where they are instructed to complete word fragments (words with missing letters) to form non-aggressive words. The word fragments are based on similar stimuli used in prior research on hostile bias (Anderson, Carnagey, & Eubanks, 2003; DeWall & Bushman, 2009). This task was validated in a previous study (WRAIR # 2574).
- b. Angry Cognitions Scale/HAB measure: This measure asks respondents to read hypothetical scenarios and indicate how they would interpret and respond to them. It was developed by Martin and Dahlen (2007) and will be used as a measure of HAB.
- c. Trait anger Scale: Brief measure of trait anger validated by Wilk et al., (2015).
- d. State Aggression Survey: This survey is adapted from several others in the literature to measure variance along the normal spectrum of aggressive behaviors in daily life that the average person might display (Álvarez-García, et al., 2016; Deffenbacher, et al., 2001; Deffenbacher, J. et al., 2002). The survey specifically asks about driving behaviors (e.g., yelling at other drivers), and public online behaviors (e.g., posting mean comments on social media), as well as generic public displays of aggression items (e.g., Gotten angry and slammed a door).

- e. State Emotion Survey: A short measure of state (current or recent) emotions over the preceding 24 hour period adapted from Goldberg et al., (2006) and Quartana and Burns (2007).
- f. Demographic questions: Volunteers will be asked to provide their age (whole number, not birth date), highest level of education, and gender. These will be used as statistical controls in analyses.

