Volunteer recruitment and data collection will be done online by ARL AI's and/or staff with assistance from volunteerscience.com (the online experimental platform). Volunteers will be recruited via Amazon Mechanical Turk (MTurk) to the experimental webpage and complete informed consent electronically. A description of this clinical trial will be available on <http://www.clinicaltrials.gov>. Additionally a copy of the informed consent may be posted to a public website no later than 60 days after enrollment is completed.

Time-point 1: Volunteers will be randomly assigned to complete either the real or fake HBMT. Volunteers will also complete a brief vignette reading HAB activity, a brief measure of trait (what is typical for them) aggression, and state (how they have felt recently) anger.

Time-point 2: Volunteers will be asked to return no sooner than 24 hours and no later than 96 hours from when they completed time-point 1 to complete a following up HAB assessment (second vignette interpretation task) and brief surveys asking about aggressive behaviors and state anger during the preceding 24 hour period.

Mechanism for inviting volunteers back to complete time-point 2: The two-time point nature of this study will be explained to volunteers in both the study advertisement and in the ICD.

Additionally, a feature on MTurk will allow the volunteerscience.com to send a daily e-mail to time-one volunteers inviting them back to time-point two. This can be done without MTurk revealing the e-mail addresses of the volunteers. The e-mail will remind volunteers to please return at any point between 24 hours and 96 hours from when they completed the first time-point.

Upon completion of each time-point, the webpage will thank volunteers for their participation. Volunteers will be paid part of the payment at the end of time-point one and the remaining payment after completing time-point two (see section 10.6).

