## **5 HYPOTHESES**

### **5.1 Primary Hypotheses**

- a. Hypothesis 1: Relative to volunteers in the fake-training condition, those volunteers who receive the real HBMT at time-point one will report less state anger and aggression at time-point two.
- b. Hypothesis 2: Effects of HBMT on state anger and aggression in daily life will be mediated by between group differences in HAB.

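### State anger is asked about the past 24 hours but answered by how characteristic of the person it is, which leaves a trait reading open and may dilute the anger comparison in Hypothesis 1

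*Combined protocol and SAP*

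**What the plan says.** Section 3.3 describes the form as "A short measure of state (current or recent) emotions over the preceding 24 hour period". In the time-point 1 paragraph the same section separates the two constructs: volunteers complete "a brief measure of trait (what is typical for them) aggression, and state (how they have felt recently) anger".

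Appendix H opens with "How well do the following statements describe how you have" and then, in bold capitals, refers to feelings over the last 24 hours. Eight items follow. One is "I have felt angry"; another asks about stress. All eight are answered on a five-point scale from "1 = Extremely uncharacteristic of me" to "5 = Extremely characteristic of me". The appendix gives no scoring rule, does not say which items make up the state-anger score, and does not tell the volunteer how the labels relate to the 24-hour frame.

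Section 5.1 puts state anger in Hypothesis 1: relative to the fake training, "those volunteers who receive the real HBMT at time-point one will report less state anger and aggression at time-point two". Section 8.8 places the form before training at time-point one and again at time-point two. Section 9.1 compares the groups on the change in state anger with a mixed-design ANOVA. Section 5.2b expects the clearest training effect on days the volunteer reports as high in stress.

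**The concern.** The stem asks a state question and the labels offer a trait answer. What is characteristic of a person is what is typical of that person, which is how Section 3.3 explains trait. Trait anger already has its own form (Appendix G).

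A volunteer who answers by typicality reports a stable property. That answer should be much the same on both occasions, so the change score analysed under Section 9.1 carries little information about the day's anger. If enough volunteers answer this way, a real training effect on anger could be missed.

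The stress item has the same labels and is the only self-reported stress measure shown. A high score could mean a stressful day or a person who is usually stressed, and hypothesis 5.2b concerns the day.

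**Working it through.** **1. The two readings side by side.** Take the anger item and four kinds of volunteer:

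| Usual self | Past 24 hours | Answer if the stem governs | Answer if typicality governs |
|---|---|---|---|
| calm | calm | low | low |
| calm | angry | high | low (1 is truthful) |
| often angry | calm | low | can be high |
| often angry | angry | high | high |

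If the stem governs, the answer follows the day. If typicality governs, it follows the person. The second row is the problem case: an angry day earns the same score as a day without anger. Nothing on the form records which reading a volunteer used.

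**2. Contrast within the protocol.** The State Aggression Questionnaire (Appendix F) also covers 24 hours but uses frequency labels, from never to five or more times. It has no such conflict, so the aggression half of Hypothesis 1 is unaffected.

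**3. The plan's own sample-size figure.** Inputs from Sections 7.2 and 9.2: d = 0.40, 100 completers per arm, 80% power, alpha 0.05. Two-sample t test with n = 100 per arm and 198 degrees of freedom:

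- noncentrality = d × √(n/2) = 0.40 × √50 = 2.83; two-sided critical value 1.972; power 80.4%
- n per arm for 80% power = 99.1, rounded up to 100, so 200 in total
- with 50% drop-out, 200 / (1 − 0.5) = 400

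The plan's 200 and 400 both reproduce two-sided. One-sided, 78 per arm would be enough (156 in total). Two-sided is also the natural basis here: with two groups and two occasions, the group-by-time F test is the square of the t test on change scores.

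**4. Illustration of dilution.** Let a share q of each arm rate typicality and show no shift. The mean difference shrinks by the factor (1 − q). Holding the SD fixed, d(q) = 0.40 × (1 − q).

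| q | d(q) | Noncentrality, d(q) × √50 | Two-sided power |
|---|---|---|---|
| 0% | 0.40 | 2.83 | 80.4% |
| 10% | 0.36 | 2.55 | 71.7% |
| 20% | 0.32 | 2.26 | 61.5% |
| 30% | 0.28 | 1.98 | 50.4% |

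**5. Sensitivity to the fixed SD.** Volunteers who repeat the same answer also have less variable change scores, which softens the loss. In the limit where their change is exactly zero, the change variance shrinks by about (1 − q), leaving out a small term for the mixing of means. Then d(q) ≈ 0.40 × (1 − q)/√(1 − q) = 0.40 × √(1 − q), that is 0.379, 0.358 and 0.335. Power is then about 76%, 71% and 65%. The table in step 4 is therefore the more pessimistic of the two cases.

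**The case against.** The strongest reply is that the stem governs. The 24-hour period is in bold capitals and the items are worded in the perfect tense. Read together, 1 simply means that the statement does not describe the volunteer's last 24 hours, and many volunteers may answer that way. This stands as far as it goes: typicality is one of two open readings. A reader might infer that the labels force a comparison with the usual self, and the documents do not support that.

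A reader might also infer that literal readers score in the wrong direction, so that the effect is partly reversed. Reversal would need less anger to produce a higher score within the same person. A usually calm volunteer may mark 1 on an angry day, but is also likely to mark low on a calm one. A volunteer rating typicality marks much the same value on both days. Either way information is lost, but the sign does not change.

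Nor is there ground to infer bias between arms. Both arms use the same form on both occasions and assignment is randomised, so the two readings should balance.

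Two further points stand. Section 3.4 lists the main endpoints as HAB and daily aggressive behaviour, without anger, so anger's primary status rests on Section 4.1 and Hypothesis 1. And d = 0.40 is half of a HAB effect (0.78), not a value set for this scale. Appendix H also has items on irritation and annoyance, and no rule says which items count, so the effect on the analysed score is unknown.

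**Conclusion.** The conflict between stem and labels is real and worth correcting. It may attenuate the state-anger comparison by an unknown amount, and it blurs the stress item behind hypothesis 5.2b. It does not affect the aggression outcome or the sample-size arithmetic, and it is not expected to create a false difference between arms.

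The power loss depends on q, which the documents do not give. At q = 10% to 30%, power falls from about 80% to between 72% and 50% with the SD held fixed, or to between 76% and 65% if typicality raters do not change at all. Both ranges assume a true d of 0.40 on the change score, 100 per arm, two-sided 0.05, and an equal q in the two arms. They show only that the design has little slack for measurement dilution. They do not forecast the trial's power.

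**What to change.** In Appendix H keep the items and the past-24-hours stem. At both time points replace the response labels with intensity labels tied to that period, for example 1 = not at all to 5 = extremely. Change both time points together, before launch, so that baseline and follow-up share one scale.

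The direct cost is editing the labels on one web form, plus the review that Section 11.3 requires for amendments to the protocol and its supporting documents. The downside is that the form, already described in Section 3.3 as adapted, moves further from the measures it came from and loses comparability with any earlier use of the same labels. Waiting costs more: once answers are collected under two readings, they cannot be separated.
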